For the secondary objective, overall and by-stratum point estimates and 95% confidence intervals are calculated for rates of spontaneous abortions, stillbirths, induced abortions (overall, elective, and therapeutic), minor congenital anomalies, serious adverse pregnancy outcomes, abnormalities detected on prenatal or postnatal ultrasounds, and other adverse outcomes (including functional deficits, alterations in fetal growth, biochemical abnormalities, transient or infectious conditions, or persistent findings in pre-term live infants that require surgical intervention) observed during the first year of life in offspring born from exposed pregnancies. Strata are comprised by earliest trimester of exposure and potentially other variables as appropriate given the sample size.

LIST OF ABBREVIATIONS

AE	Adverse Event
AEMP	Adverse Event Management Plan
CDC	Centers for Disease Control and Prevention
CEDD	Corrected Estimated Date of Delivery
CFR	Code of Federal Regulations
CI	Confidence Interval
CIOMS	Council for International Organizations of Medical Sciences
CRF	Case Report Form
DRF	Data Resolution Form
EDD	Estimated Date of Delivery
EDOC	Estimated Date of Conception
FDA	Food and Drug Administration
FM	Fibromyalgia
GPP	Good Pharmacoepidemiology Practices
HCP	Healthcare Provider
ICH	International Conference on Harmonization
ID	Identifier
IRB	Institutional Review Board
ISPE	International Society for Pharmacoepidemiology
LMP	Last Menstrual Period
MACDP	Metropolitan Atlanta Congenital Defects Program
NCHS	National Center for Health Statistics
NICU	Neonatal intensive care unit
NIH	National Institutes of Health
OTC	Over-the-Counter
OTIS	Organization of Teratogen Information Services
PDA	Patent Ductus Arteriosus
PFO	Patent Foramen Ovale
RS	Research Specialist
RM	Records Management
SAC	Scientific Advisory Committee
WIRB	Western Institutional Review Board

TABLE OF CONTENTS

PR	ото	COL SIGNATURE PAGE	II
RE	GIST	RY CONTACT INFORMATION	III
SY	NOP	SIS	IV
LIS	ST OF	ABBREVIATIONS	VII
TΑ	BLE	OF CONTENTS	.VIII
1.	INTE	RODUCTION	1
	Bacl	kground	1
2.	PUR	POSE AND RATIONALE	3
3.	REG	SISTRY DESIGN	4
4.	REG	SISTRY POPULATION	4
	4.1	Eligibility Criteria	4
	4.2	Minimum Criteria for Registry Enrollment	4
5.	GEN	NERAL REGISTRY PROCEDURES	5
	Sum	mary of Evaluations	6
	5.2	Sources of Reports	7
	5.3	Registration Process	7
		5.3.1 Information Collected at Registration	7
	5.4	Prenatal Follow-up Evaluation	9
		5.4.1 Timing of Interim Prenatal Follow-Up	9

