6.2.3 Evaluable Registry Reports

An evaluable report is a case, submitted or verified by a HCP, containing at least the minimum criteria for Registry enrollment, and is not lost to follow-up. Prospectively reported evaluable cases with known outcomes are included in the primary analyses for the Interim Report produced annually and the Final Report. Retrospective reports are summarized separately in the Interim Reports and the Final Report.

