7. OUTCOME CLASSIFICATION, EVALUATION AND MONITORING

7.1 Definitions

7.1.1 Pregnancy Outcome

Pregnancy outcomes are classified into one of the following mutually exclusive categories:

- Live birth full-term (≥ 37 weeks)
- Live birth pre-term (<37 weeks)
- Stillbirth
- Spontaneous abortion
- Induced abortion
 - Therapeutic
 - Elective
- Ectopic pregnancy
- Molar pregnancy
- Maternal/fetal death

Definitions of the individual outcome categories are located in the Glossary beginning on page 35.

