8.5 Data Analysis

8.5.1 Birth Defects

For the primary analysis, the prevalence of birth defects reported to the Registry in the evaluable population is calculated by dividing the number of birth defects (i.e., the number of pregnancy outcomes occurring at or after 20 weeks gestation with a noted birth defect) by the total number of live births in the evaluable population. Pregnancy losses with reported birth defects occurring at or after 20 weeks gestation are included in the numerator of the estimate of risk for birth defects to increase sensitivity and to allow for comparison with the MACDP which calculates rates using this convention. A secondary analysis is conducted including pregnancy losses with reported birth defects occurring at any gestational age in the calculation of risk. An additional secondary analysis will be performed that only includes birth defects that are noted from ultrasound examinations (pre-natal or post-natal). Birth defects will be reported by outcome (live birth (overall and full-term or pre-term)), stillbirth, induced abortion (elective or therapeutic) and trimester of exposure. All defects detected <20 weeks of gestation will be described in the report. Additionally, birth defects noted by non-HCP reports will be reported descriptively.

Calculations of 95% confidence intervals (two-sided) for individual birth defect rates are based on the exact method using binomial probability distribution. The prevalence in exposed cases is compared with the observed prevalence in the MACDP (Correa et al., 2007). In addition, one-sample binomial tests at the two-sided 0.05 level are used to test the association of elevated levels of major birth defects in pregnancy exposures to Savella by comparing the observed proportion of birth defects in the Registry with rates from the MACDP.

Enrolled pregnancies that are LTFU without pregnancy outcome, as defined in section 6.2.6, will be enumerated in the interim/final report, but will not be included in the

calculation of risk. Prospectively enrolled pregnancies with an outcome will be included in the calculation of risk regardless of whether they are subsequently designated as infant LTFU.

If feasible, comparisons between the Registry and an appropriate external comparison group will be examined.

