8.5.3 Adverse Pregnancy Outcomes

Overall and by-stratum point estimates of rates and 95% confidence intervals will be calculated for the following outcomes:

- Spontaneous abortions
- Stillbirths
- Induced abortions (overall and elective or therapeutic)
- Minor congenital anomalies,

Other adverse pregnancy outcomes among pregnancies exposed to Savella and their live births during the first year of life will be summarized as counts and percentages of the total number of prospective evaluable outcomes. Summaries will also be presented by subgroups including maternal age at conception (<25, 25-35, >35), family history of birth defects, smoking status, and alcohol use during pregnancy. Additional subgroups may be analyzed if deemed appropriate and necessary given the sample size. These other adverse pregnancy outcomes include:

- Functional deficits
- Alterations in fetal growth
- Transient or infectious conditions
- Biochemical abnormalities
- Pre-term infants with findings that persist and require surgical intervention

Strata are comprised by earliest trimester of exposure and potentially other variables as appropriate given the sample size, such as maternal age, history of birth defects, lifestyle variables, comorbidities, and concomitant drug exposures.

All chromosomal abnormalities, whether classified as a birth defect or other adverse outcome, will be displayed in a separate listing.

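### Section 8.5.3 expresses infant outcomes as percentages of all evaluable pregnancy outcomes, which understates them, and omits the 95% CIs that the synopsis promises

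*Protocol*

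**What the plan says.** Section 8.5.3 treats two groups of outcomes differently. Spontaneous abortions, stillbirths, induced abortions and minor anomalies get point estimates with 95% CIs, overall and by stratum. The remaining outcomes, including those of live births in the first year of life, "will be summarized as counts and percentages of the total number of prospective evaluable outcomes". The list is functional deficits, alterations in fetal growth, transient or infectious conditions, biochemical abnormalities, and pre-term infants with persisting findings that need surgery. The section adds: "Summaries will also be presented by subgroups including maternal age at conception", followed by family history of birth defects, smoking and alcohol.

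The composition of the denominator comes from other sections:

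- Section 6.2.3 makes a report evaluable if it is submitted or verified by a provider, meets the minimum criteria and is not lost to follow-up. It sets no live-birth condition: "Prospectively reported evaluable cases with known outcomes are included in the primary analyses".
- Section 7.1.1: "Pregnancy outcomes are classified into one of the following mutually exclusive categories". The categories include spontaneous and induced abortion, ectopic pregnancy and molar pregnancy. Section 8.2 repeats these.

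For birth defects, section 8.5.1 instead divides "by the total number of live births in the evaluable population".

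The synopsis (Statistical Methods, secondary objective) says that "overall and by-stratum point estimates and 95% confidence intervals are calculated for rates of spontaneous abortions" and continues the same list to "other adverse outcomes (including functional deficits, alterations in fetal growth, biochemical abnormalities, transient or infectious conditions" and the pre-term surgery item. It then says "Strata are comprised by earliest trimester of exposure".

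**The concern.** A pregnancy that ends in an abortion, or is ectopic or molar, cannot contribute a functional deficit or an infection in infancy. Putting it in the denominator adds nothing to the numerator and lowers the percentage. These items are collected mainly on the Pediatric Follow-Up Form, which is completed only after a live birth (sections 5.6.1 and 5.6.2). Section 8.6 explains that losses without a detected defect are kept out of the birth-defect risk because they may misclassify it; section 8.5.3 does not apply that reasoning to outcomes that are harder still to assess in a loss.

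First-year infant outcomes are a named secondary objective, and section 8.2 makes descriptive statistics the main approach, so for these items the percentage is the result. The error always runs toward reassurance. It also varies with the share of losses, so groups with equal infant risk but different loss rates would show different percentages. Separately, two parts of the same document disagree on whether these percentages carry an interval.

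**Working it through.** **Inputs.** From section 8.4: 350 prospective pregnancies, 10% lost to follow-up, 62% of recognized pregnancies ending in a live birth, 196 live births expected. One outcome per pregnancy is assumed throughout.

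**The plan's own figure.** Evaluable outcomes: 350 × 0.90 = 315. Live births: 315 × 0.62 = 195.3, against 196 stated. The figure reproduces to within one.

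**Overall dilution.** Shown percentage = rate among live births × live-birth share. The share is 196/315 = 0.62, so about 119 of 315 outcomes (38%) are not live births. Illustrative counts (assumed), with exact (Clopper-Pearson) 95% CIs:

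| Affected infants | Over 315 | Over 196 live births |
|---|---|---|
| 5 | 1.6% | 2.6% (0.8% to 5.9%) |
| 10 | 3.2% | 5.1% (2.5% to 9.2%) |
| 20 | 6.3% (3.9% to 9.6%) | 10.2% (6.3% to 15.3%) |

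**Range for the live-birth share.** The 62% is a general-population figure, and section 5 allows enrollment at any time in pregnancy, so the registry's share may be higher. A 10% rate among live births would show as:

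- share 0.62: 6.2%
- share 0.70 (assumed): 7.0%
- share 0.80 (assumed): 8.0%
- share 0.90 (assumed): 9.0%

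**Infants without pediatric follow-up.** Section 6.2.7 defines a separate infant lost-to-follow-up category. The protocol gives no rate for it. If 90% to 60% of 196 live births are followed (assumption), 176 to 118 infants are assessed, and the factor relative to assessed infants falls from 176/315 = 0.56 to 118/315 = 0.37. Dividing by all live births would leave part of this dilution in place: with 80% followed (157 infants), 10 cases are 10/157 = 6.4% of those assessed but 10/196 = 5.1% of live births.

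**Unequal dilution between groups.** The Glossary places spontaneous abortion before 20 weeks, and section 8.2 starts the third trimester at 28 weeks, so a pregnancy first exposed in the third trimester cannot end in one. With equal infant rates, the apparent first-to-third-trimester ratio equals the ratio of live-birth shares. Taking 0.62 to 0.90 for first-trimester and 0.95 to 1.00 for third-trimester exposure (assumptions, apart from 0.62), it runs from 0.62/1.00 = 0.62 to 0.90/0.95 = 0.95. The same mechanism applies to the subgroups named in 8.5.3 if their loss rates differ.

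**Pre-term surgery item.** If 10% to 15% of 196 live births are pre-term (assumption), that is 20 to 29 infants. Three cases would be 3/20 = 15.0% to 3/29 = 10.3% of pre-term live births, but 3/315 = 1.0% as 8.5.3 would report them.

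**Confidence intervals.** The synopsis puts these outcomes in the list of rates with overall and by-stratum 95% CIs. Section 8.5.3 confines CIs to its first list. The general remark in section 8.2 that intervals serve estimation does not assign one to these outcomes, so the conflict stands.

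**The case against.** Several counterarguments have weight.

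- **The composition is inferred.** Section 8.5.3 does not name abortions, ectopic or molar pregnancies, and section 6.2.3 defines an evaluable report rather than an evaluable outcome. Section 6.2.7 recognizes an infant portion of the registry and keeps losses to follow-up out of the statistical analyses, so an infant-level reading is arguable. The literal wording still points to all evaluable outcomes.
- **Trimester strata are not certain for these items.** A reader might infer that 8.5.3 commits to a trimester comparison that will falsely favor early exposure. The documents do not support that. The synopsis stratifies these outcomes, but 8.5.3 attaches strata to its first list and leaves it unclear whether its closing sentence on strata covers the second. Section 8.2 only permits trimester stratification, and the number first exposed in the third trimester is not given. The distortion is conditional.
- **Some rescaling is possible.** Sections 8.5.1 and 8.5.2 plan birth-defect rates by trimester and maternal age, so live-birth denominators for those groups should be recoverable. Family history, smoking and alcohol are not covered, and live births are not the same as infants assessed.
- **The CI conflict can be read the other way.** Section 2 separates outcomes to be estimated from outcomes to be summarized, and 8.5.3 largely follows that split. Correcting the synopsis would also restore agreement. No decision depends on these intervals.
- **The outcomes are secondary and descriptive**, and most of the illustrative magnitudes rest on assumptions. Both are true.

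Leaving the matter to the statistical analysis plan is not a full answer: the protocol states a denominator, and a plan that corrected it would depart from the protocol.

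**Conclusion.** The point holds for the secondary infant summaries. As worded, 8.5.3 shows infant outcomes at about 0.62 of their rate among live births on the planning inputs, and at about 0.9 if the live-birth share is 90% (assumption). Infants without pediatric follow-up lower the figure further if they stay in the denominator. Groups with different loss rates are distorted unequally; for trimester strata this applies only if they are presented as the synopsis says, and the apparent ratio of 0.62 to 0.95 rests on assumed shares. The 62% is a planning value, so 0.62 should not be read as the bias that the registry will actually have. The CI mismatch is a genuine inconsistency within the protocol, but of wording only.

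A reader might also infer that the birth-defect result is compromised. It is not: section 8.5.1 uses live births, and the primary estimate, sample size and error rates are untouched.

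**What to change.** In section 8.5.3:

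1. For infant outcomes, divide by live-born infants with pediatric follow-up for the item and time point, leaving out infants lost to follow-up as section 6.2.7 defines them. For the surgery item, divide by assessed pre-term live births.
2. Show that number overall and in each stratum or subgroup.
3. List growth alteration in losses at or after 20 weeks separately, or add assessable losses to both numerator and denominator, so that a growth-restricted stillbirth is not dropped.
4. Make the synopsis and 8.5.3 agree on CIs, preferably by giving exact two-sided 95% CIs as the synopsis states, and say whether trimester strata apply to these items.

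The cost is a wording change and minor programming on data already collected. Percentages will be larger than in earlier interim reports, so the next report needs a note explaining the new denominator.

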8.5.4 Infant Follow-Up

Descriptive statistics will be presented for infant outcomes including mean gestational age at outcome, mean birth weight, medications, head circumference, APGAR scores, immediate post-natal health problems requiring resuscitation or admission to the NICU, and developmental milestones

8.6 Potential Biases

Because early prenatal testing is so prevalent in the US, it may be difficult to achieve adequate numbers of prospectively identified patients if all pregnancies with prior prenatal testing are excluded from the analysis. Therefore, the primary analyses includes pregnancies enrolled prior to outcome but after a prenatal test as long as the test does not indicate an abnormality. However, this practice could potentially bias the results by lowering the overall risk of birth defects (Honein et al., 1999). The analysis attempts to address whether this practice biases the results.

As reporting of pregnancies is totally voluntary, it is possible that even in prospectively reported cases, potential bias could exist. For example, high-risk pregnancies or low-risk pregnancies may be more likely to be reported.

Enrolled pregnancies that have reached their estimated date of delivery and for which outcome information is unobtainable are considered "lost to follow-up". It is possible that outcomes among pregnancies lost to follow-up could differ from those with documented outcomes. Because of differences in follow-up and reporting patterns, it is currently not possible to assess with any certainty what impact the potential biases the losses to follow-up may have on the analysis. However, efforts at comparing some of the characteristics of each group are conducted in an attempt to address this potential source of bias.

Following the MACDP convention, calculation of birth defect risk excludes fetal losses (spontaneous abortions, induced abortions, stillbirths, etc.) for which no birth defects have been detected as they may introduce a classification bias. It is unknown what percentage of these pregnancies consists of potentially normal outcomes or birth defects. The Registry attempts to obtain information on birth defects detected at the time of the outcome. However, the reporting physician may not know the condition of the aborted fetus.

While the Registry analysis is limited to prospective reports, some pregnancy exposures are reported following pregnancy outcome (retrospective cases). Each retrospective report is carefully reviewed. In general, retrospective reports of exposures to therapy following notification of outcome are biased toward reporting the severe and unusual

cases and are not reflective of the general experience with the medication. Moreover, information about the total number of exposed persons is not known. Therefore, rates of outcomes cannot be calculated from these data. However, a series of reported birth defects can be evaluated to detect patterns of specific birth defects and can help to identify early signals of therapy risks.

9. **REGISTRY ADMINISTRATION**

9.1 Regulatory Agency Reporting Considerations

The Registry follows the FDA Guidance for Industry, *Establishing Pregnancy Exposure Registries* (FDA, 2002) for regulatory reporting of adverse events to FDA. "The Agency considers pregnancy exposure registry reports (both prospective and retrospective) as derived from active solicitation of patient information." Therefore Allergan is responsible for, "reporting any serious and unexpected events by regulatory definition and where a reasonable possibility exists that the drug or biological product caused the adverse event within 15 calendar-days" (FDA, 2002).

For FDA status reporting, the Registry Interim Report can be appended to the annual report submission as described in the FDA Guidance (FDA, 2002). The Interim Report, published annually, contains the background, Registry design, and analysis plan. It summarizes the status and the cumulative data on the Registry to date. In addition, the Registry can generate individual case line listings to assist Allergan in preparation of its submission. The Interim Report, generated annually, is cumulative and current to the most recent data cutoff period.

9.2 Reporting of Adverse Events

Reports of pregnancy exposures to Savella are carefully reviewed for reports of any adverse events.

The Registry systematically collects information on major structural and chromosomal defects that are apparent at birth and noted through infant age one (1) year, as well as other specified fetal and maternal outcomes. Information on events not routinely collected is sometimes reported to the Registry. These data are of limited utility since the Registry does not systematically collect them. HCPs are encouraged to report such events to the manufacturer.

The Registry reports all adverse pregnancy outcomes including birth defects, spontaneous fetal losses, and induced abortions (elective or therapeutic), maternal and non-defect fetal events regardless of attribution, temporal association, or seriousness, for Registry participants, to Allergan Global Drug Safety department, which forwards the reports to the regulatory authorities in accordance with federal regulations. Specifically, Allergan will:

 Report any unexpected fatal or life-threatening adverse experiences associated with use of the drug by telephone or fax no later than 7 calendar days after initial receipt of the information [21 CFR 312.32(c)(2)];

- Report any serious, unexpected adverse experiences, as well as results from animal studies that suggest significant clinical risk, in writing to this Division and to all investigators within 15 calendar days after initial receipt of this information [21 CFR 312.32(c)(1)]; and
- Submit annual progress reports within 60 days of the anniversary of the date that the IND went into effect (the date clinical studies were permitted to begin) [21 CFR 312.33].

10. ETHICAL CONSIDERATIONS

10.1 Institutional Review Board/Ethics Committee

According to the FDA Guidance document (FDA, 2002), registries such as this must comply with ethical principles and regulatory requirements involving human subject's research. Therefore, institutional review board (IRB) approval is necessary. Notification of the Board's approval of the Registry must be provided to Allergan or its designee.

The Registry protocol is submitted for initial review, annual review, and amendments as necessary to Western Institutional Review Board (WIRB), [name], [contact].

10.2 Ethical Conduct of the Registry

This Registry is conducted in compliance with the Registry protocol, International Society for Pharmacoepidemiology's (ISPE) Guidelines for Good Pharmacoepidemiology (2004), US FDA regulatory requirements, ISPE's Data Privacy, Medical Records Confidentiality and Research in the Interest of Public Health (1998), and in accordance with the ethical principles of the Declaration of Helsinki (1995).

10.3 Waiver of Documentation of Consent

Based on the following regulations a waiver of documentation of consent is appropriate for this Registry.

As stated in the US Code of Federal Regulations (CFR) 21 CFR 56.109 (and additionally in 45 CFR 46.117(c)(2)):

"(c) An IRB shall require documentation of informed consent in accordance with 50.27 of this chapter, except as follows:

(1) The IRB may, for some or all subjects, waive the requirement that the subject, or the subjects legally authorized representative, sign a written consent form if it finds that the research presents no more than minimal risk of harm to subjects and involves no procedures for which written consent is normally required outside the research context.

(d) In cases where the documentation requirement is waived under paragraph (c)(1) of this section, the IRB may require the investigator to provide subjects with a written statement regarding the research."

The research involves no more than minimal risk to the subjects. This is an observational Registry that involves no experimental intervention and poses no possibility of physical harm. The only potential risk is a breach of confidentiality, and the Registry has well-established procedures in place to prevent any such breach of confidentiality. As described above, extensive safeguards are in place to assure that patients' privacy is protected:

- a) An adequate plan is provided to protect the identifiers from improper use and disclosure (See section 12.5).
- b) An adequate plan is provided to remove the identifiers at the earliest opportunity.
- c) Adequate assurances are provided that the protected health information will not be reused or disclosed to any other person or entity.

The research involves no procedures for which written consent is normally required outside the research context. Enrollment in this observational Registry is strictly voluntary. The schedule of patient visits and treatment regimens are at the complete discretion of the treating physician. Data submitted to the Registry is limited to data routinely collected and documented in the patient's medical record.

